### **Human Subjects Protection**

#### **Subject Recruitment Methods**

Subjects scheduled for surgery and to have a preoperative visit in our Preoperative Assessment Clinic (PAC) will be identified using their medical information in our EHR (Epic) to see if they fit our study criteria, and interviewed by research staff in the PAC. We ensure equal access to participation among women and minorities because we see both who fit our study criteria adequately on a daily basis. We will protect the privacy of potential subjects during recruitment by not using names or date of birth, and we will assign a unique study identifier to their medical record number.

- We do not plan to use recruitment flyers and advertisements.
- We will use limited PHI to identify subjects via medical records search.
  - We will use only the minimum amount of PHI necessary to review eligibility criteria and method to contact potential subjects. The information we plan to collect for this purpose includes:
    - Medical history
    - Planned surgical procedure

- Age
- PAC appointment time

Confidentiality/privacy will be protected prior to ascertaining desire to participate. Subjects who appear to be eligible for the study on the PAC appointment list will be marked for a conversation with a member of the study staff that will occur during their PAC visit. If they do not wish to participate, any record of their PHI will be immediately erased if electronic or shredded if on paper. **Informed Consent**

Signed informed consent will be obtained from each subject by a member of the study staff while the patients are present in the PAC.

### **Confidentiality and Privacy**

Confidentiality will be protected by collecting only information needed to assess study outcomes, minimizing to the fullest extent possible the collection of any information that could directly identify subjects, and maintaining all study information in a secure manner. To help ensure subject privacy and confidentiality, only a unique study identifier will appear on the data collection form. Any collected patient identifying information corresponding to the unique study identifier will be maintained on a linkage file, stored separately from the data. The linkage file will be kept secure, with access limited to designated study personnel. Following data collection subject identifying information will be destroyed by securely wiping data 3 years after closure of the study, consistent with data validation and study design, producing an anonymous analytical data set. Data access will be limited to study staff. Data and records will be kept locked and secured, with any computer data password protected. No reference to any individual participant will appear in reports, presentations, or publications that may arise from the study.

### **Data and Safety Monitoring**

Since this is a feasibility study of the Caretaker monitor, we will disable the data screen from displaying vital signs. Stored data will later be analyzed for proximity to standard vital signs measured during the subject's hospital stay. No vital signs from the monitor will be used for actionable interventions.

The principal investigator will be responsible for the overall monitoring of the data and safety of study participants. The principal investigator will be assisted by other members of the study staff.

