## **Methods and Measures**

### **Design**

The Caretaker device is a wrist device that has a version that has already been approved by the FDA for use amongst medical professionals. For the conduct of this protocol we propose to use a newer version of the device called VitalStream, which has been cleared for use by the FDA.

The New Caretaker device being used in the study has successfully passed all safety and accuracy tests by an independent lab, which have been submitted to the FDA already (see attached Declaration of Conformity).

We plan to monitor ambulatory preoperative CareTaker VS (HR, RR, SaO2, BP, Cardiac Output, Stroke Volume, and HRV) in random patients who meet our inclusion criteria for 18-24 hours, beginning during their preoperative (Preoperative Assessment Clinic, PAC) visit then overnight after they leave. Postoperatively, we will measure these VS in the same patients for approximately 24 hours postoperatively.

These monitors transmit VS to a data cloud, where we will be able to store and then later analyze the VS data. Clinical data will be collected from our EPIC Information System in order to provide pre- and postoperative information to examine corresponding risk factors and provide demographics.

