### **SUBSTUDY**

Since our hypotheses are 1) the percent of time the patient experiences significantly abnormal or concerning preoperative vital signs (VS) values will correlate with a higher risk for a similar range of VS postoperatively, and 2) undesired outcomes such as myocardial infarction or higher 30-day readmission rates, we need to assure that the CareTaker monitors we use have relative accuracy. This will be important to help assure that the CareTaker device measures will be generalizable to the current standards used in clinics.

In order to investigate the accuracy and precision of heart rate (HR), systolic blood pressure (SBP), diastolic blood pressure (DBP), and oxygen saturation (SpO2) measurements of the CareTaker monitoring devices we are using, we plan to compare the values obtained by CareTaker devices to standard clinic VS measurements.

In order to accomplish this, we will measure VS using hospital-grade standard monitors at intake into the Preoperative Assessment Clinic. We will then discuss the study with the patient. If the patient accepts entry to the study, we will then place the CareTaker monitor on the patient and record the VS. We will then recheck VS with standard monitors every 20 minutes while the patient is in clinic. Within 60

seconds, each VS measure will be immediately followed by recording the VS from the CareTaker monitor.

---

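### The CareTaker screen is disabled without exception, yet the accuracy substudy needs a CareTaker reading within 60 seconds of each clinic measurement, and the source of that reading is not stated

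*Combined protocol and SAP*

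**What the plan says.** Three parts of the combined protocol and SAP bear on this.

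- **Data and Safety Monitoring.** The screen is to show no vital signs: "we will disable the data screen from displaying vital signs". The reason given is "Since this is a feasibility study of the Caretaker monitor". A retrospective comparison is planned: "Stored data will later be analyzed for proximity to standard vital signs measured during the subject's hospital stay". The section adds: "No vital signs from the monitor will be used for actionable interventions".
- **Substudy.** Standard monitors are used at clinic intake. If the patient agrees to take part, "we will then place the CareTaker monitor on the patient and record the VS". Standard readings are then repeated at 20-minute intervals until the patient leaves. The CareTaker step that goes with each has a limit of 60 seconds and is worded as follows: "each VS measure will be immediately followed by recording the VS from the CareTaker monitor". The measures compared are heart rate, systolic and diastolic pressure, and oxygen saturation.
- **Design.** On data capture: "These monitors transmit VS to a data cloud, where we will be able to store and then later analyze the VS data".

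No section says who records the substudy's CareTaker values, from what source (device screen, separate display or stored data), or whether the screen stays on until the patient leaves the clinic. The Analytical Plan does not mention the substudy.

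**The concern.** The substudy is there to show that the devices are accurate enough to carry the main hypotheses, so how its pairs are formed matters. A site that follows both sections as written meets a screen that shows no vital signs and an instruction to record those vital signs at once. The protocol does not tell it what to do.

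The likely improvisations each have a cost:

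- **Screen left off, no times logged.** The CareTaker values may exist in the cloud, but matching them to the standard readings becomes uncertain. Times that were never logged may not be recoverable.
- **Screen switched on in clinic.** The CareTaker value is recorded just after the standard one. If the recorder knows the standard value, the choice of which CareTaker value to write down is no longer independent of it, and agreement can look better than it is. Monitor values also become visible during preoperative assessment, which makes the commitment not to act on them harder to keep.

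Different staff could reasonably choose differently, so the pairs could come from a mixture of procedures.

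**Working it through.** No arithmetic applies: the point depends on no sample size, power or event figure. The check sets the sections side by side.

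1. **Does the disabled screen cover the clinic period?** The Setting section starts monitoring in the PAC, and Data and Safety Monitoring makes no exception for time or place. As written, yes.
2. **Is the substudy recording a live step?** It is placed in a sequence: standard reading, then CareTaker recording, at once and within 60 seconds. A device that transmits its data for storage would not need a separate recording step after each standard reading. The natural meaning is a contemporaneous read-off, although the text does not say that a displayed value is read or copied.
3. **Does the planned stored-data comparison already cover the substudy?** Not expressly. It is against standard vital signs from the hospital stay, whereas the substudy readings are taken at the PAC visit.
4. **Can both instructions be met?** Yes, if the paired value is taken from the transmitted data and matched by time to the standard reading. The Design section describes the storage route, which needs no visible screen.
5. **Does the protocol supply what that route needs?** Retrospective matching needs three things: the clock time of each standard reading, device and clinic clocks that agree, and a rule for which value or values in the window count. None is specified in the Substudy section or the Analytical Plan.
6. **Would values seen in clinic fall within the assessment?** The Interventions and Interactions section places consent in the PAC before the preoperative visit, and the substudy readings repeat for as long as the patient is in clinic. The Background says that a single snapshot of vital signs is generally used to judge fitness for surgery. An enabled display could therefore be seen while that judgement is being made.
7. **How large is the effect?** It cannot be derived. The documents give neither the length of the clinic visit, and so the number of pairs at 20-minute intervals, nor any figure for reader bias.

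**The case against.** The strongest reply is that there is no contradiction, only a missing sentence. The values go to a cloud store, a stored-data comparison is already planned for the hospital stay, and recording from the monitor can mean capturing its data. This stands in part: the two sections can be reconciled, and a reader who infers that one of them must fail goes further than the documents allow. It does not remove the point, because the route is not applied to the substudy and its matching requirements are absent.

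Several other inferences are tempting but unsupported:

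- **That the disabled screen is a blind.** The protocol does not call it one. The reason it gives is that this is a feasibility study.
- **That one person takes both readings.** The Substudy section names no recorder. Knowledge of the reference value is a possibility, not a stated procedure.
- **That staff would choose among beat-to-beat values.** No section says what the device outputs at that resolution, and the brochure is a separate attachment.
- **That every pair in all 150 evaluable patients (up to 200 consented) is either missing or compromised.** This holds only if the cloud route is ruled out, and it is not.

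It is also fair to say that the commitment on actionable interventions governs use, not visibility. Standard monitors in clinic would normally show a concerning value anyway. A visible CareTaker value therefore strains that commitment but does not by itself breach it. Finally, device accuracy is not among the listed outcomes, and the primary outcomes (data capture and monitor return) are not affected.

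**Conclusion.** The two sections conflict on their natural reading and should be reconciled. The consequence is limited to the validity of the paired accuracy comparison and, if the display is enabled in clinic, to possible influence on preoperative assessment. The direction of a reader bias would be towards better apparent agreement. Its size is unknown and cannot be derived from the documents.

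This rests on two assumptions. One is that the recording step in the Substudy section means a contemporaneous read-off, which is its ordinary sense but is not spelled out. The other is that the stored record carries usable time stamps, which the Design section does not state and the sponsor should confirm. The point is worth acting on because extraction by a fixed rule is a better method than a live read-off and is cheap. It is not a proven failure of either procedure.

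**What to change.** Amend the Substudy section to say:

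- The screen stays disabled throughout the clinic visit.
- Staff log the clock time of each standard reading, with clinic clocks synchronised to the device.
- The paired CareTaker value is extracted afterwards from the time-stamped stored record by a fixed rule stated in advance, for example using the 60 seconds after the logged time, with the way values in that window are summarised also stated.

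Add a cross-reference from Data and Safety Monitoring, so that its stored-data comparison expressly includes the PAC readings.

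The cost is protocol wording, one time-log field and clock synchronisation. Pairs with a data gap in the window will be lost, and their number should be reported. No separate embargo on the cloud record is needed, since the Confidentiality and Privacy section already restricts data access to study staff. The change is most useful before enrolment or early in it, because unlogged reading times may be unrecoverable.

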**Objectives**

Using a portable, wireless multi-Vital Sign (VS) monitoring system developed by Caretaker Medical, we have several objectives:

- Primary:
  - Assess the feasibility of placing a Caretaker monitor on subjects scheduled for surgery for an 18-24 hour preoperative ambulatory monitoring session.
  - Assess the feasibility of placing a Caretaker monitor on subjects scheduled for surgery for the perioperative period defined as 18-24 hour intraoperative and postoperative ambulatory monitoring session.
  - Quantitate the data capture rate (estimated at over 99% in the company's prior studies) in this setting and how reliable our monitor return rate is in this setting.
- Secondary:
  - Assess the prevalence of alterations in VS (HR, RR, SaO2, BP, Cardiac Output, Stroke Volume, and HRV preoperatively) in a group of our highest acuity patients (top quartile of risk score) undergoing non-cardiac surgical procedures requiring at least a 2-day admission.
  - Assess any correlation of concerning ambulatory preoperative VS to postoperative VS.
    - We estimate that the percent of time the patient experiences these concerning preoperative VS values will correlate with a higher risk for a similar range of VS postoperatively, as well as undesired outcomes.
      - Undesired outcomes are defined as a) 30-day mortality, b) longer length of stay, c) higher ICU transfer, and 4) RRT calls).

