### **Setting**

The subjects will be recruited in the PAC, where their monitoring period will start, and will continue at their residence (or wherever they decide to stay that night). They will return the monitor with them into the holding area on the day of their surgical procedure. We will replace their monitor on them in the Post-Anesthesia Care Unit (PACU) where it will remain with the patient for 24 hours +/- 6 hours continuously monitoring.

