**Outcome Measure(s)**

- Primary outcomes:
  - Phase I: Quantitate the data capture rate and how reliable our monitor return rate is in this setting.
  - Phase 2: Quantitate the data capture rate in this setting for the perioperative period.
- Secondary:
  - Assess the prevalence of alterations in VS (HR, RR, SaO2, BP, Cardiac Output, Stroke Volume, and HRV preoperatively) in a group of our highest acuity patients (top quartile of our internal PAC risk score) undergoing non-cardiac surgical procedures requiring at least an overnight admission. See Table 2 for ranges.

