### **Analytical Plan**

- For the feasibility portion of the study, we will describe descriptive results of subjects' time of use of the monitor, their description of ease of use (difficult or easy), and the quantity of non-artifactual VS data.
- Results will be analyzed initially using descriptive statistics (percent of time VS remained in one of the ranges listed in Table 2) and means/standard error.
- We will compare relative incidence with matched cohort undergoing surgery using univariate analyses (categorical variables: chi-square test, continuous variables: Student's t-test or Mann-Whitney U test). We will use multivariable Cox proportional hazards regression modeling to assess VS risk factors associated with the postoperative undesired outcomes mentioned in outcome measures above.
- Statistical methods data will be expressed as mean  $\pm$  SD, number (percentage), odds ratio, and 95% CI. All P values will be two-tailed, and a P value less than 0.05 is considered significant.

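### The Phase 2 capture rate cannot show whether signal loss falls in abnormal periods, because the plan states no use for hospital readings taken while the monitor had no valid signal

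*Combined protocol and SAP*

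**What the plan says.** - **Hospital readings.** Data and Safety Monitoring says: "Stored data will later be analyzed for proximity to standard vital signs measured during" the hospital stay. Proximity is not defined there, and there is no pairing rule and no rule for a hospital reading without a CareTaker partner.
- **Primary outcome.** Outcome Measure(s) gives "Phase 2: Quantitate the data capture rate in this setting for the perioperative period". Objectives has the wider form: "Quantitate the data capture rate (estimated at over 99% in the company's prior studies) in this setting". No denominator or success threshold is given.
- **Analysis.** The Analytical Plan describes feasibility partly through "the quantity of non-artifactual VS data", with no rule for what counts as artifact and no breakdown by vital-sign range. The vital-sign results start from "percent of time VS remained in one of the ranges listed in Table 2".
- **Other comparisons.** Design draws EPIC data for risk factors and demographics. The Substudy compares CareTaker with standard monitors, but it is paired by design and confined to the clinic.

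**The concern.** Percent of time in a range can be computed only from readings that were captured and kept. If the monitor loses signal more often when the vital sign is abnormal, the kept readings under-represent the outer ranges, and one overall capture figure does not reveal it. A wrist device might behave this way during low perfusion, shivering, agitation or arrhythmia; the documents neither show nor exclude it.

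The study aims at patients with severe abnormality. Its secondary analyses relate time in concerning ranges to postoperative vital signs and to undesired outcomes, so the outer ranges carry much of the interest. Hospital readings taken while the monitor was silent are the direct evidence of what it missed in Phase II, and no planned analysis uses them for that purpose.

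**Working it through.** **The plan's figure.** The figure of over 99% is the company's estimate from its prior studies. No derivation is given, so there is nothing to reproduce. The sample size of 150 is used below only as a count of patients.

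**1. Illustration of selective loss (assumed inputs).** Let p be the true share of time in a range, c_in the capture inside it and c_out the capture elsewhere.

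- Overall capture = p·c_in + (1 − p)·c_out
- Recorded share = p·c_in / overall capture

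| p | c_in | c_out | Overall capture | Recorded share | Shortfall |
|---|---|---|---|---|---|
| 2% | 60% | 99.9% | 0.0120 + 0.9790 = 99.1% | 0.0120/0.9910 = 1.2% | 0.8 points, about 40% relative |
| 2% | 80% | 99.9% | 0.0160 + 0.9790 = 99.5% | 0.0160/0.9950 = 1.6% | 0.4 points, about 20% relative |

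**2. Worst-case bound.** Suppose capture c is measured over all intended time and every lost minute lies in the range. Then recorded share = (p − min(p, 1 − c))/c. At c = 0.99:

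| True share | Worst recorded share | Shift (points) |
|---|---|---|
| 1% or less | 0 | up to 1.0 |
| 2% | 0.01/0.99 = 1.0% | 1.0 |
| 5% | 0.04/0.99 = 4.0% | 1.0 |
| 10% | 0.09/0.99 = 9.1% | 0.9 |

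For p at or above 1 − c the shift is (1 − c)(1 − p)/c. It is largest at p = 1 − c, where it equals 1 − c, or 1 point. Over 24 hours, 1% is 14.4 minutes.

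**3. Pooled and per-patient rates.** Setting gives the postoperative period: "it will remain with the patient for 24 hours +/- 6 hours continuously monitoring". Taking 24 hours, 150 patients give 3,600 hours. If 8 patients each lost a 4-hour abnormal episode (32 hours), pooled capture would be 1 − 32/3,600 = 99.1%. Each of those patients would have capture of 20/24 = 83.3%, so the bound on their own percent of time is 16.7 points, not 1.

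**4. What a check on hospital readings could detect (assumed inputs).** Take 6 charted readings per patient, 150 × 6 = 900, of which 5% (45) are in an abnormal range. Compare capture in the 45 with 99% in the other 855: two-sided 5% test, normal approximation for two proportions, pooled variance under the null. A design effect of 2 halves both counts.

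| Capture in abnormal readings | Power, independent readings | Power, design effect 2 |
|---|---|---|
| 90% | 0.89 | 0.73 |
| 80% | 0.99 | 0.94 |

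The standard error of a 90% capture rate on 45 readings is √(0.9 × 0.1/45) = 4.5 points, or 6.3 points with design effect 2 (4.5 × √2). With 90% capture in the 45 and 99.5% in the other 855, overall capture is (40.5 + 850.7)/900 = 99.0%.

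**The case against.** - **Silence is not a rule.** A reader might infer that the plan discards unmatched hospital readings. It does not say so; it states no use for them. This stands, and the point is worded accordingly.
- **The mechanism is assumed.** A reader might also infer that the monitor does fail when patients are unwell. Nothing in the documents shows this, and the inputs in steps 1 and 4 are assumptions. This stands: the point is that the plan cannot tell, not that bias is present.
- **Capture is itself a bound.** A reader might conclude that the plan leaves the bias unbounded. Measured over intended time, 99% capture limits the shift to about 1 point, and the 40% relative loss is only 0.8 points. This stands, but it depends on a denominator that the plan does not define, and a pooled rate does not give the bound for each patient.
- **99% is not a pass mark.** It is the company's expectation, so a rate above it does not make the study a success under the plan. This stands.
- **The main hypothesis is preoperative.** It rests on time in ranges during Phase I at home, where no standard readings exist, so the check cannot reach that exposure. This stands as a limit on the fix.
- **The study is descriptive.** The display is disabled and no value is acted upon, so a capture rate answers the stated primary question. That is fair, but a rate that cannot separate random gaps from loss in abnormal periods says little about use in high-risk patients, and the added table is cheap.

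**Conclusion.** The concern holds as a gap in the analysis plan. The only stated use of in-hospital standard vital signs requires a CareTaker value, and no analysis compares capture between normal and abnormal readings. If loss is concentrated in abnormal periods, percent of time in the outer Table 2 ranges is understated.

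The absolute size is at most about 1 percentage point at 99% capture of intended time. That is minor for common ranges. It can erase a range holding 1% or less of a patient's time, or halve one holding 2%. The exposure is larger if the denominator omits unworn or non-transmitting time, where the bound no longer applies, or for single patients with long gaps behind a good pooled rate. The bound is arithmetic; the 2.0% to 1.2% illustration and the power figures rest on the stated assumptions. A cheap addition is worth making, but nothing here shows that the planned results are in fact biased.

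**What to change.** In the Analytical Plan:

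1. **Define capture.** Use intended monitoring time as the denominator, state the rule for a valid (non-artifactual) value, and report capture per patient as well as pooled. Setting has the monitor replaced in the PACU, while Interventions and Interactions includes intraoperative monitoring; reconcile these so that intended Phase II time is fixed.
2. **Use every hospital reading.** Take all charted standard readings during intended Phase II wear, paired or not. Report the proportion with a valid CareTaker value within a prespecified time window, by Table 2 range for heart rate, systolic pressure, diastolic pressure and respiratory rate, with confidence intervals that allow for clustering by patient. Table 2 has no ranges for the other parameters. Its boundary values also need assigning first: a heart rate of 50 and a systolic pressure of 90 fall in no range, and a diastolic pressure of 65 falls in two.
3. **Prespecify the reading.** If capture is clearly lower in an outer range, report percent of time in that range as a likely underestimate. Do not re-weight by inverse capture: the weights would come from charted ranges but be applied to CareTaker ranges, and agreement between the two is still under study.

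**Cost:** a few lines and one table, from hospital readings that the plan already intends to use. **Downsides:** outer-range cells will be imprecise, charted times may be inexact, and the check covers Phase II only.
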